14.2 Demographic and Baseline Characteristics

The following demographic variables will be summarized: age, sex, skeletal age, and clinical histories.

14.3 Analysis of Primary Endpoint

Two-sided Student's t-test will be employed for the primary endpoint.

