SAFETY EVALUATIONS	Since the device does not pose greater than minimal risk, neither an adverse event (AE) or serious adverse experience (SAE) is expected. Unanticipated risks will be reported to the IRB, in accordance with IRB standards.
PLANNED INTERIM ANALYSES	N/A
STATISTICS Primary Analysis Plan	
 1. Detect differences in the primary endpoint between Experiment and Control arms, using a two-sided Student t-test. 2. Detect differences in the secondary endpoint between Experiment and Control arms, using a Wilcoxon rank-sum test.
Rationale for Number of Subjects	Targeting a power of 0.75, statistical tests achieved a power of 0.79 to detect a difference of 0.50 months for 1600 interpretations.

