4 STUDY DESIGN

4.1 Study Overview

This is a prospective, multi-center, randomized controlled trial. 1600 interpretations by consented radiologists are planned.

Each of the interpreted studies will be assigned at random to one of two arms: Experiment or Control. The AI model will populate the radiologists' report templates for studies assigned to the Experiment arm. The AI model will not populate the radiologists' report templates for studies assigned to the Control arm.

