5 CRITERIA FOR EVALUATION

5.1 Primary Efficacy Endpoint

The primary endpoint is mean absolute difference between dictated final impressions and the consensus determination of a panel of radiologists.

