8 STUDY TREATMENTS

8.1 Method of Assigning Subjects to Treatment Groups

Studies will be assigned at random to Experiment or Control treatment groups in a 1:1 ratio using the Python random package.

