8.2 Blinding

Due to the objectives of the study, the identity of Experiment and Control treatment groups will be known to radiologists.

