8.4 Supply of Study Device at the Site

The device will be installed at the investigational sites one time prior to randomization by the Investigator. The device will receive studies from the sites, perform randomization, and populate the radiologists' report templates for studies assigned to the Experiment arm for the duration of the study.

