10 EVALUATIONS BY VISIT

The device records individual visits.

1. Receive the study as a DICOM file.
2. Record the study as a DICOM file.
3. Randomizes the study.
4. Perform and record the AI model.
5. If randomized into the Experiment arm, populate the radiologists' report template with the AI model.

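### The primary t-test ignores radiologist and site; a random-intercept model costs almost nothing, and a radiologist-clustered sensitivity analysis would cover an AI effect that varies between radiologists

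*Combined protocol and SAP*

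**What the plan says.** Section 14.3 gives the whole primary analysis in one sentence: "Two-sided Student's t-test will be employed for the primary endpoint". The synopsis agrees: "Detect differences in the primary endpoint between Experiment and Control arms, using a two-sided Student t-test". Neither names a covariate, and no other section adds a radiologist or site term, stratification, a clustered analysis or any sensitivity analysis.

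The outcome is defined per interpretation (5.1): "The primary endpoint is mean absolute difference between dictated final impressions and the consensus determination of a panel of radiologists". The unit of randomization is the imaging study (4.1: "Each of the interpreted studies will be assigned at random to one of two arms: Experiment or Control"; 8.1: "Studies will be assigned at random to Experiment or Control treatment groups in a 1:1 ratio using the Python random package"). Allocation happens inside the device when a study arrives (8.4: "The device will receive studies from the sites, perform randomization, and populate"). Radiologists are not blinded (8.2: "the identity of Experiment and Control treatment groups will be known to radiologists").

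The synopsis gives 6 sites. Section 14.6 gives power 0.79, against a target of 0.75, for a difference of 0.50 months with 1600 interpretations. It gives no SD, alpha, number of radiologists or intraclass correlation (ICC).

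**The concern.** Radiologists will normally read in both arms. With 5 reads, the chance of having at least one in each arm is 1 - 2 × 0.5^5 = 0.94. Three things follow.

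- **Efficiency.** Stable accuracy differences between radiologists stay in the t-test's error term, although the design allows them to be removed.
- **Balance over readers.** The t-test needs the reader of a study to be unrelated to its arm. The device randomizes on receipt and fills the template, radiologists know the arm, and the documents do not say how a study reaches a radiologist. The text therefore does not secure this condition.
- **Generalization.** If the AI helps some radiologists more than others, and the conclusion is meant for radiologists in general, the t-test's standard error is too small. A random intercept alone does not cure this.

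At stake are some power, protection against uneven spread of arms over readers, and whether the result can be said to hold for other radiologists.

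**Working it through.** **Inputs from the documents:** 1600 interpretations, 1:1 (800 per arm), difference 0.50 months, power 0.79, 6 sites.

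**Assumptions, none in the documents:** two-sided alpha 0.05; 30-100 radiologists, with 12 (2 per site) as a low case; ICC 0-0.20; SD of the AI effect between radiologists 0.25 or 0.5 months; caseload coefficient of variation (CV) 0 or about 1.

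**Step 1: the plan's figure.** With no SD or alpha stated, 0.79 can only be back-solved. SD = 0.50 / [(1.960 + 0.806) × √(2/800)] = 0.50/0.1383 = 3.615; the noncentral t gives 3.613 (3.59-3.64 allowing for rounding of 0.79). Hence SE0 = 3.613 × 0.05 = 0.1806. Check: Φ(0.50/0.1806 - 1.96) = Φ(0.81) = 0.79.

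**Step 2: power with a random intercept, common AI effect.** With K radiologists reading m studies each, residual variance σ² and between-radiologist variance τ², information = 0.25(K-1)/(σ² + mτ²) + 0.25K(m-1)/σ². For K = m = 40 and ICC 0.10: total variance 3.615² = 13.07, σ² = 11.76, τ² = 1.307. Information = 0.25 × 39/64.0 + 0.25 × 40 × 39/11.76 = 0.15 + 33.16 = 33.31. Power = Φ(0.50 × √33.31 - 1.96) = Φ(0.926) = 0.82. With unequal caseloads (CV about 1) and site terms:

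| ICC | 12 radiologists | 30 | 60 | 100 |
|---|---|---|---|---|
| 0 | 0.789 | 0.789 | 0.789 | 0.789 |
| 0.05 | 0.808 | 0.806 | 0.803 | 0.801 |
| 0.10 | 0.828 | 0.826 | 0.822 | 0.818 |
| 0.20 | 0.869 | 0.866 | 0.862 | 0.858 |

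Simulation with estimated variance components (4000 replicates per cell) gives these changes against the t-test: 0 to -0.002 at ICC 0, then +0.010 to +0.015, +0.030 to +0.036 and +0.063 to +0.073. Type I error is 0.043-0.056 (t-test 0.042-0.055). Skewed (half-normal) residuals give 0.045-0.048 for both.

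Fixed radiologist effects would cost more. At ICC 0 their power is 0.784, 0.779, 0.763 and 0.734 with 20, 40, 100 and 200 radiologists. That is the reason for a random intercept.

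**Step 3: arms unevenly spread over radiologists (simulated).** Let the Experiment share differ between radiologists with SD 0.10, unrelated to accuracy, at ICC 0.05-0.10. Type I error is 0.060-0.094 for the t-test and 0.050-0.052 for the random intercept. If share correlates 0.5 with accuracy, bias is 0.15-0.22 months for the t-test and 0.02-0.07 for the random intercept: reduced, not removed.

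**Step 4: AI effect varying between radiologists, inference to radiologists in general.** For the t-test, Var = SE0² + s²(1 + CV²)/J, with effect SD s and J radiologists, and type I error = 2Φ(-1.96 × SE0/√Var). Example with s = 0.5, J = 30, CV = 1: Var = 0.0326 + 0.25 × 2/30 = 0.0493; √Var = 0.222; type I error = 2Φ(-1.594) = 0.111.

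| Effect SD (months) | CV | 12 radiologists | 30 | 60 | 100 |
|---|---|---|---|---|---|
| 0.25 | 0 | 0.069 | 0.057 | 0.054 | 0.052 |
| 0.25 | 1 | 0.088 | 0.065 | 0.057 | 0.054 |
| 0.5 | 0 | 0.126 | 0.080 | 0.065 | 0.059 |
| 0.5 | 1 | 0.194 | 0.111 | 0.080 | 0.068 |

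For 30-100 radiologists a nominal 95% interval thus covers 93.5-94.8% (SD 0.25) or 88.9-94.1% (SD 0.5). The random intercept alone does about the same in simulation (0.049-0.067 and 0.058-0.114). CR2 clustered standard errors with Satterthwaite degrees of freedom give 0.044-0.054. Plain cluster-robust errors are not enough with few readers: with 20 radiologists, effect SD 0.5 and unequal caseloads they ran at 0.087.

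**The case against.** The strongest reply is that nothing in the plan is wrong. Randomization is by study, and with a common effect the t-test holds its level: 0.044-0.060 in a separate simulation over ICC 0-0.20. The stated power already exceeds the target, and every magnitude above depends on inputs the documents lack. At SD 3.61, ICCs of 0.05, 0.10 and 0.20 mean that radiologists' average errors differ with SD 0.81, 1.14 and 1.62 months, or 1.6 to 3.2 times the target difference. An effect SD of 0.5 months equals the whole target difference. The uneven-share scenario is hypothetical: the plan does not describe radiologists choosing studies by arm.

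All of that stands, and it is why the point is put as an improvement and why the gain may be small. It does not argue for keeping the t-test as primary, because the alternative loses almost nothing when radiologists do not differ. The 0.002 loss is the largest simulated value, not a proven bound.

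A second objection also stands. If the AI effect really varies, the clustered analysis has low power. At effect SD 0.5 and CV 1, Step 4's variance with Satterthwaite degrees of freedom of 5.8, 14.6, 29 and 47 gives about 0.34, 0.56, 0.67 and 0.71 for 12, 30, 60 and 100 radiologists. All are below 0.75. This limits that analysis to a supporting role and should be disclosed.

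**Conclusion.** The concern holds as an improvement that should be made; confidence is medium. The unadjusted t-test is valid under a common AI effect and arm-independent reading. A random radiologist intercept with site terms matches its power at ICC 0 and gains roughly 1 to 7 points over ICC 0.05-0.20. It also removes most of the distortion if arms are unevenly spread over readers.

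Neither model supports a claim about radiologists in general if the AI effect varies. The t-test's excess type I error is slight at effect SD 0.25 months with 30 or more radiologists, and material at 0.5 months with few radiologists. These sizes rest on the assumed alpha, the back-solved SD and the assumed radiologist numbers, caseloads, ICC and effect SD. The direction of the recommendation does not depend on their exact values.

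**What to change.** In 14.3 and the synopsis, replace the t-test with wording to this effect: the primary analysis is a linear mixed model of the per-interpretation absolute difference in months, with fixed effects for arm and site and a random intercept for radiologist, reporting the adjusted mean difference and 95% CI. Sensitivity analyses are (a) the two-sided Student's t-test and (b) the same comparison with radiologist-clustered CR2 standard errors and Satterthwaite degrees of freedom. Name the degrees-of-freedom method for the primary model, and say that it reduces to arm plus site if the radiologist variance is estimated as zero.

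In section 10 or 15.1, state that radiologist identifier and site are stored with each interpretation. Section 15.1 provides for data on each radiologist, but the device steps in section 10 list no identifier. In 14.6, give the SD and alpha used, and say that 0.79 assumes independent interpretations and a common AI effect. Whether the conclusion is for the participating radiologists or for radiologists in general is the investigators' choice; (b) is the analysis that speaks to the latter.

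The cost is SAP wording, a little more analysis and confirmation of the identifier. The estimand barely moves: at ICC 0.05-0.20, 0.4-4.6% of the weight shifts away from caseload shares. If the AI effect changed by 0.25 months per SD of caseload, the estimate would move by at most 0.008 months on average. Analysis (b) gives a wider interval: with a common effect, ICC 0 and unequal caseloads, its power is 0.73-0.78 with 30-100 radiologists and 0.63 with 12. While (b) stays a sensitivity analysis, the sample size does not need to change.

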9.1.2 Demographics

Demographic information (date of birth, gender, race) will be collected retrospectively.

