14.6 Sample Size and Randomization

Targeting a power of 0.75, statistical tests achieved a power of 0.79 to detect a difference of 0.50 months for 1600 interpretations.

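### The primary t-test leaves out age, sex and the recorded AI prediction: no bias results, but a nearly free precision gain of unknown, possibly very small, size is given up

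*Combined protocol and SAP*

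**What the plan says.** The primary analysis is one sentence in 14.3: "Two-sided Student's t-test will be employed for the primary endpoint". The synopsis (Statistics, Primary Analysis Plan, item 1) matches it: "Detect differences in the primary endpoint between Experiment and Control arms, using a two-sided Student t-test". No covariate, adjusted model or stratified analysis appears anywhere in the document.

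The outcome, from 5.1: "The primary endpoint is mean absolute difference between dictated final impressions and the consensus determination of a panel of radiologists".

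Three candidate covariates will be available:

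- **Age and sex.** Section 9.1.2: "Demographic information (date of birth, gender, race) will be collected retrospectively". Their only stated use is descriptive, in 14.2: "The following demographic variables will be summarized: age, sex, skeletal age, and clinical histories".
- **AI-predicted skeletal age.** Section 10, step 4, has no arm condition: "Perform and record the AI model". Only step 5 depends on arm: "If randomized into the Experiment arm, populate the" radiologist's template. The prediction will therefore exist for control studies too.

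The sample-size statement in 14.6, repeated in the synopsis, is: "Targeting a power of 0.75, statistical tests achieved a power of 0.79 to detect a difference of 0.50 months for 1600 interpretations". Neither place gives an SD, an alpha or any covariate correlation.

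**The concern.** In a randomized comparison, a covariate that predicts the outcome and cannot be changed by the assigned arm can be used to shrink the standard error of the arm difference without changing what is estimated. Here three such values will be in the database and none is used.

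Age and sex are fixed before assignment. The AI prediction is computed just after randomization (step 4 follows step 3), but section 1 describes it as made from the hand radiograph, so arm should not alter its value.

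What is at stake is the width of the interval for the arm difference and, through it, power. The choice has to be made in advance, because an adjusted model picked after the data are seen would not carry the same weight as a pre-specified one.

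**Working it through.** **Inputs from the documents.** 1600 interpretations allocated 1:1 (8.1), so about 800 per arm; difference 0.50 months; stated power 0.79; target power 0.75 (14.6).

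**Assumptions.** Two-sided alpha 0.05; independent interpretations; R² (the share of outcome variance explained by the covariates) of 0.02, 0.05 or 0.10. The SD is back-solved, not given.

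**Step 1: the plan's own figure.** The 0.79 cannot be verified without an SD and alpha, but the SD it implies can be found. The standard error of the difference is SD × √(2/800) = 0.05 × SD. Power of 0.79 needs 0.50/SE ≈ 1.961 + 0.806 = 2.767, so SE ≈ 0.1807 and SD ≈ 3.61 months (noncentral t gives 3.613). Rounding of 0.79 allows 3.59 to 3.64.

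**Step 2: adjustment.** The residual SD is SD × √(1−R²), so standard error and interval shrink by that factor. Half-width = 1.961 × 0.05 × 3.613 × √(1−R²). Equivalent unadjusted N = 1600/(1−R²).

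| Assumed R² | √(1−R²) | 95% half-width (months) | Narrowing | Power | Equivalent N |
|---|---|---|---|---|---|
| 0 | 1.000 | 0.354 | none | 0.790 | 1600 |
| 0.02 | 0.990 | 0.351 | 1.0% | 0.798 | 1633 |
| 0.05 | 0.975 | 0.345 | 2.5% | 0.810 | 1684 |
| 0.10 | 0.949 | 0.336 | 5.1% | 0.830 | 1778 |

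The percentage narrowing does not depend on alpha or SD. Power does, slightly: at R² of 0.10 it is 0.839 if alpha is 0.01 (implied SD about 2.95) and 0.826 if alpha is 0.10 (implied SD about 4.08).

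**Step 3: is that R² range sensible?** The outcome is an unsigned error, which age predicts only if the spread of errors changes with age. As an illustration, take normal signed errors whose scale rises linearly by a factor r over a uniform age range. A linear age term then has R² = (2/π)(r−1)²/12 divided by E[s²] − (2/π)(E[s])², where s is the scale. For r = 2 this is 0.0531/(2.333 − 1.432) ≈ 0.06. For r = 1.5 and r = 3 it is about 0.02 and 0.12. This is hypothetical; the documents do not say how errors vary with age.

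**Step 4: bias and cost.** In a simulation with 3000 trials per setting, skewed independent errors and a true difference of −0.50, the unadjusted estimate averaged −0.501 to −0.504 and type I error was 0.048 to 0.055. At R² = 0, adding up to 8 covariate terms leaves power at 0.790.

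**Step 5: if the AI effect varies by radiologist.** Patient covariates do not reduce that part of the variance. If w is the share of the variance of the estimate that they can act on, the factor becomes √(1−wR²). At R² of 0.10, narrowing of 3% rather than 5% corresponds to w = (1 − 0.97²)/0.10 ≈ 0.59. So √(1−R²) is a best case.

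**The case against.** The strongest reply is that there is no defect. An unadjusted two-sided t-test is an acceptable pre-specified analysis in a 1:1 randomized trial, the stated power already exceeds the plan's target, and the value of adjustment rests on an R² that the documents do not give. All of that stands, and it fixes the weight of the point. It does not remove it: the values are already to be collected, and if they explain nothing, almost nothing is lost.

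Three narrower objections also stand, and the fix below reflects them:

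- The factor √(1−R²) requires independent interpretations. With six sites and radiologists who may each read many studies, the gain may be less.
- The AI run follows randomization. If a failed run were noticed and repeated mainly where a template should be filled, missingness would depend on arm. The documents do not address this.
- If the t-test becomes a supporting analysis, the power statement no longer describes the primary analysis and needs a label.

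A reader might infer more: that leaving out covariates biases the comparison, that the t-test is invalid for that reason, or that the trial is underpowered. The documents support none of these. Randomization protects the unadjusted mean difference, and 0.79 is above the stated 0.75 target. Nor do they support a large gain; no R² is given from which to promise one.

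**Conclusion.** The point holds as an optional improvement. Sections 14.3 and the synopsis fix an unadjusted analysis while age, sex and an arm-independent AI prediction will be available for both arms. The loss is one of precision only: roughly 1% to 5% of interval width over the assumed R² range, or a rise in power from 0.790 to between about 0.798 and 0.830. An R² of about 0.025 would bring power to 0.80.

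These figures rest on an assumed alpha of 0.05, a back-solved SD, independent interpretations and an assumed R². The true gain could be close to zero. Confidence is high that no covariate is planned and medium that using them would help noticeably.

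**What to change.** In 14.3 and in the synopsis primary analysis plan, pre-specify:

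- A linear model for the absolute difference with arm, chronological age, sex and recorded AI-predicted skeletal age (a quadratic term in age is optional), reporting the arm difference with a robust standard error and 95% confidence interval.
- The unadjusted difference as a supporting analysis.
- No adjustment for the dictated skeletal age, which arm can affect. Section 14.2 lists skeletal age without saying which one is meant, so name it.
- Missing covariates filled with the mean pooled over arms, so that no study is dropped. Use a missing indicator only for age and sex.
- The AI prediction as a covariate only if it is run, and re-run after any failure, identically in both arms.

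If clustering by radiologist or site is also handled, which is a separate question, put these covariates in that same single model. In 14.6 and the synopsis sample-size row, state that the power of 0.79 refers to the unadjusted test.

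The cost is wording in four places, a little more analysis work and a negligible loss of degrees of freedom. No new data are needed.

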14.4 Analysis of Secondary Endpoints

Wilcoxon rank-sum test will be employed for the secondary endpoint.

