5.2 Secondary Efficacy Endpoints

- Radiologist interpretation time.

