15 DATA COLLECTION, RETENTION AND MONITORING

15.1 Data Collection Instruments

The Investigator will prepare and maintain adequate and accurate documents designed to record all observations and other pertinent data for each radiologist.

The Investigator is responsible for all information collected on radiologists enrolled in this study. All data collected during the course of this study must be reviewed and verified for completeness and accuracy by the Investigator.

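### The rank-sum test for interpretation time ignores which radiologist read the study, which may cost power if readers differ in speed and the time saving is modest

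*Combined protocol and SAP*

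**What the plan says.** The secondary analysis is described in two places. The synopsis (Statistics, Primary Analysis Plan) has "Detect differences in the secondary endpoint between Experiment and Control arms, using a Wilcoxon rank-sum test", and section 14.4 has "Wilcoxon rank-sum test will be employed for the secondary endpoint". Neither mentions a stratum, a covariate or a radiologist effect, and no other section supplies one.

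The endpoint in section 5.2 is "Radiologist interpretation time". It is the only secondary endpoint and the only measure of the efficiency objective in section 3.2.

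On allocation, section 4.1 says "Each of the interpreted studies will be assigned at random to one of two arms: Experiment or Control", and section 8.1 says "Studies will be assigned at random to Experiment or Control treatment groups in a 1:1 ratio using the Python random package". The unit of randomization is therefore the single study. Section 4.1 also gives the size: "1600 interpretations by consented radiologists are planned".

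The only power statement, in section 14.6, is "Targeting a power of 0.75, statistical tests achieved a power of 0.79 to detect a difference of 0.50 months for 1600 interpretations". It is in months of skeletal age, so it belongs to the primary endpoint. The documents give no number of radiologists, no spread of reading times and no target time saving.

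**The concern.** When studies are randomized one by one, each radiologist with more than a few reads contributes reads to both arms and can serve as his or her own control. A pooled rank-sum test discards this. It ranks a slow reader's studies against a fast reader's, and habitual speed then widens the spread of ranks in both arms and dilutes a given proportional time saving.

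At stake is the trial's only answer on efficiency. If readers differ clearly in speed and the AI saves perhaps 5-10% of reading time, the planned test could miss an effect that a stratified test on the same data would find more often. Choosing a stratified test after the data are seen would look selective, so the choice belongs in the plan.

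**Working it through.** **The plan's own figure.** With 800 reads per arm, the standard error of a difference in means is SD × √(2/800) = 0.05 × SD. The documents state no SD and no alpha, so 0.79 cannot be reproduced directly. At an assumed two-sided 5% level it implies SD = 0.50 / [0.05 × (1.960 + 0.806)] = 3.61 months. This says nothing about power for interpretation time.

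**Inputs.** From the documents: 1600 reads, 1:1 allocation by study, 6 sites. Assumed: two-sided alpha 0.05; log-normal times; within-radiologist SD of log time 0.6; between-radiologist SD 0, 0.3, 0.6 or 0.8; 15, 30, 60 or 100 radiologists with uneven workloads.

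**Hand approximation.** An 8% saving is a shift of −ln(0.92) = 0.0834 in log time. Power ≈ Φ(0.0834 / (0.05 × SD) − 1.96). The pooled test works against the total SD, √(0.6² + between²); the stratified test works against about 0.6.

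| Between SD | Total SD | Pooled | Stratified |
|---|---|---|---|
| 0 | 0.600 | Φ(2.78 − 1.96) = 0.79 | 0.79 |
| 0.3 | 0.671 | Φ(2.49 − 1.96) = 0.70 | 0.79 |
| 0.6 | 0.849 | Φ(1.97 − 1.96) = 0.50 | 0.79 |
| 0.8 | 1.000 | Φ(1.67 − 1.96) = 0.39 | 0.79 |

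This treats the tests as comparisons of mean log time and ignores the cost of small strata, so it slightly flatters stratification.

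**Simulation.** The pooled rank-sum test was set against a van Elteren test using the strata proposed below, with 2000 runs per cell. Ranges are over the number of radiologists.

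| Saving | Test | Between SD 0 | 0.3 | 0.6 | 0.8 |
|---|---|---|---|---|---|
| 5% | Pooled | 0.39-0.40 | 0.30-0.33 | 0.22-0.24 | 0.18-0.19 |
| 5% | Stratified | 0.34-0.39 throughout | | | |
| 8% | Pooled | 0.77-0.80 | 0.68-0.70 | 0.49-0.51 | 0.38-0.43 |
| 8% | Stratified | 0.75-0.78 | 0.74-0.77 | 0.71-0.76 | 0.70-0.77 |
| 15% | Pooled | ≥0.99 | ≥0.99 | ≥0.96 | ≥0.88 |
| 15% | Stratified | ≥0.99 throughout | | | |

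At a 20% saving the pooled test has at least 0.98 power throughout.

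**Validity.** With no AI effect, rejection was 0.036-0.061 (pooled) and 0.038-0.061 (stratified).

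**Feasibility.** Between 89% (100 radiologists) and 98% (15 radiologists) of radiologists had reads in both arms, and they carried 98.8-100% of reads.

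**Another parameterization.** Fix the effect at about 0.14 total SD and let radiologists explain 30% of the variance. Pooled versus stratified power is then 0.77 versus 0.90 with 40 equal-volume radiologists, and 0.78 versus 0.84 with 90 of unequal volume (300 runs, so error of 2 to 3 points).

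**The case against.** **The planned test is legitimate.** An unstratified rank-sum test is simple and valid, the endpoint is secondary, and no power was promised for it. This stands, and it is why the point is an improvement and not an error.

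**The size rests on undocumented inputs.** The gain depends on the ratio of between- to within-radiologist spread. For an 8% saving with 30 and 100 radiologists, a within-SD of 0.9 and between-SD of 0.3 give no gain (pooled 0.40 and 0.38, stratified 0.38 and 0.38). A within-SD of 0.4 and between-SD of 0.6 give a gain of over 30 points (0.63-0.64 versus 0.97). This also stands, but it is largely a rescaling of cases already shown. Multiplying the first case by 0.6/0.9 turns it into a 5.4% saving with between-SD 0.2.

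**The effect may vary by reader.** If the AI effect averages zero but varies between radiologists (SD 0.1 in log time), both tests reject too often: 0.09-0.12 pooled and 0.12-0.13 stratified with 30 radiologists, and about 0.17 and 0.18 with 15. Stratifying does not cure this and is slightly worse. Either result then applies to the participating radiologists only.

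**The reader may not be fixed before randomization.** Sections 8.4 and 10 have the device randomize when it receives the study, and section 8.2 leaves the arm known to radiologists. If arm influenced who reads, the stratum would no longer be independent of arm. That is no defence of the pooled test, which would then mix reader speed with the AI effect. The plan should say how readers are assigned.

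**Reader identity is not listed among the device's records.** Section 10 names neither reader nor reading time. Section 15.1 plans documents "designed to record all observations and other pertinent data for each radiologist", which makes the link plausible but does not state it. The sponsor should confirm it.

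**Conclusion.** The concern holds as a conditional loss of efficiency. The plan randomizes studies individually, names no radiologist stratum for its only efficiency endpoint, and so leaves a within-reader comparison unused. Under the stated assumptions, an 8% saving with between-radiologist SD 0.6 loses about 20 to 25 points of power; with SD 0.3, about 5 to 8. For a 5% saving both tests are weak, and for 15% or more the planned test usually succeeds. The loss therefore matters only where a modest saving meets sizeable differences between readers. Whether this trial falls there cannot be settled from the documents. The change is worth making because the possible gain is much larger than the possible cost. Confidence is medium.

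**What to change.** Replace the text of section 14.4, and align the synopsis, along these lines:

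> Interpretation time will be compared between arms with a two-sided van Elteren (stratified Wilcoxon) test. Each radiologist with at least 10 reads and at least one read in each arm is a stratum; all other radiologists are merged into one stratum per site. The ratio of geometric mean times (Experiment/Control) with 95% CI will be estimated from a linear model of log time with the same strata as fixed effects. The unstratified rank-sum test is a sensitivity analysis.

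Also state the significance level, how a radiologist who reads at several sites is placed, and how readers are assigned to studies. A merged stratum with one arm empty needs no special rule, because it contributes nothing to the test.

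**Cost.** SAP wording only, once the sponsor confirms that each read carries its radiologist's identity. If radiologists do not differ in speed, an 8% saving loses about 1 point of power with 15 or 30 radiologists, 2 with 60 and 4 with 100; allow 1 to 5.

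**Further gain.** Section 14.4 currently promises no effect estimate. With 30 radiologists, the 95% CI for the time ratio is the estimate multiplied and divided by 1.061 with strata, against 1.067, 1.085 and 1.100 without strata at between-radiologist SD 0.3, 0.6 and 0.8. Coverage is 94-96% either way.
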